16.4. Sponsor Responsibilities

All information and data sent to BSC concerning subjects or their participation in this study will be considered confidential by BSC. Only authorized BSC personnel or a BSC

representative including, but not limited to Contract Research Organization (CRO) will have access to these confidential records. Authorized regulatory personnel have the right to inspect and copy all records pertinent to this study. Study data collected during this study may be used by BSC for the purposes of this study, publication, and to support future research and/or other business purposes. All data used in the analysis and reporting of this study will be without identifiable reference to specific subject name.

Boston Scientific will keep subjects' identifiable health information confidential in accordance with all applicable laws and regulations. Boston Scientific may use subjects' health information to conduct this research, as well as for additional purposes, such as overseeing and improving the performance of its device, new medical research and proposals for developing new medical products or procedures, and other business purposes. Information received during the study will not be used to market to subjects; subject names will not be placed on any mailing lists or sold to anyone for marketing purposes.

16.4.1. Role of Boston Scientific Representatives

Boston Scientific personnel can provide technical support to the investigator and other health care personnel (collectively HCP) as needed during implant, testing required by the protocol, and follow-ups. Support may include HCP training, addressing HCP questions, or providing clarifications to HCPs concerning the operation of BSC equipment/devices (including programmers, analyzers, and other support equipment).

At the request of the investigator and while under investigator supervision, BSC personnel may operate equipment during implant or follow-up, assist with the conduct of testing specified in the protocol, and interact with the subject to accomplish requested activities. Typical tasks may include the following.

- Interrogating the device or programming device parameters to investigator-requested settings as well as operating equipment
- Performing lead diagnostic testing using a Pacing System Analyzer or programmer to obtain pacing and sensing thresholds and impedance measurements
- Clarifying device behavior, operation or diagnostic output as requested by the investigator or other health care personnel
- Assisting with the collection of study data from Pacing System Analyzers, programmers, and other equipment
- Entering technical data on technical source form as long as the responsible investigator verifies and signs the completed worksheet
- Print out programming reports directly from the clinician programmer and provide original to clinical site as source documentation
- Provide technical expertise/support to subjects during office visits and/or during teleconference calls/electronic communications with the principal investigator or their delegated site staff and the subject.

In addition, BSC personnel may perform certain activities to ensure study quality. These activities may include the following.

- Observing testing or medical procedures to provide information relevant to protocol compliance
- Reviewing collected data and study documentation for completeness and accuracy

Boston Scientific personnel will not do the following.

- Practice medicine
- Provide medical diagnosis or treatment to subjects
- Discuss a subject's condition or treatment with a subject without the approval and presence of the investigator
- Independently collect critical study data (defined as primary or secondary endpoint data)
- Enter data in electronic data capture systems or on paper case report forms

16.5. Insurance

Where required by local/country regulation, proof and type of insurance coverage, by BSC for subjects in the study will be obtained.

17. Monitoring

Monitoring will be performed during the study to assess continued compliance with the protocol and applicable regulations. In addition, the clinical research monitor verifies that study records are adequately maintained, that data are reported in a satisfactory manner with respect to timeliness, adequacy, and accuracy, and that the Principal Investigator continues to have sufficient staff and facilities to conduct the study safely and effectively. The Principal Investigator/institution guarantees direct access to original source documents by BSC personnel, their designees, and appropriate regulatory authorities.

The study may also be subject to a quality assurance audit by BSC or its designees, as well as inspection by appropriate regulatory authorities. It is important that the Principal Investigator and relevant study personnel are available during on-site monitoring visits or audits and that sufficient time is devoted to the process.

18. Potential Risks and Benefits

18.1. Anticipated Adverse Events

The following anticipated adverse events (AE) for the SMART Registry subjects are the same as any other subject implanted with a CRT-D system and not participating in any study.

Table 18.1-1: Potential Adverse Events for Implantation of a Pulse Generator and/ or Lead System

Potential Adverse Events for Implantation of a Pulse Generator and/ or Lead System	
Air embolism	Lead dislodgment
Allergic reaction	Lead fracture
Bleeding	Lead insulation breakage or abrasion
Bradycardia	Lead perforation
Cardiac tamponade	Lead tip deformation and / or breakage
Chronic nerve damage	Local tissue reaction
Component failure	Loss of capture
Conductor coil fracture	Myocardial Infarction (MI)
Death	Myocardial necrosis
Elevated thresholds	Myocardial trauma (e.g., tissue damage, valve damage)
Erosion	Myopotential sensing
Excessive fibrotic tissue growth	Oversensing / undersensing
Extracardiac stimulation (muscle/ nerve stimulation)	Pacemaker-mediated tachycardia (PMT) (Applies to dual-chamber devices only.)
Failure to convert an induced arrhythmia	Pericardial rub, effusion
Fluid accumulation	Pneumothorax
Foreign body rejection phenomena	Pulse generator migration
Formation of hematomas or seromas	Shunting current during defibrillation with internal or external paddles
Heart block	Syncope
Heart failure following chronic RV apical pacing	Tachyarrhythmias, which include acceleration of arrhythmias and early, recurrent atrial fibrillation
Inability to defibrillate or pace	Thrombus, thromboemboli
Inappropriate therapy (e.g., shocks, and antitachycardia pacing [ATP] where applicable, pacing)	Valve damage
Incisional pain	Vasovagal response
Incomplete lead connection with pulse generator	Venous occlusion
Infection including endocarditis	Venous trauma (e.g. perforation, dissection, erosion)
Insulating myocardium during defibrillation with internal or external paddles	Worsening heart failure

Please refer to the specific CRT-D device Physician's Technical Manual for additional information.

Subjects may develop psychological intolerance to a pulse generator system and may experience the following:

- Dependency
- Depression
- Fear of premature battery depletion
- Fear of shocking while conscious
- Fear that shocking capability may be lost
- Imagined shocking
- Fear of device malfunction

18.2. Anticipated Adverse Device Effects

Adverse Device Effects that are part of the listing in the previous 18.1 section are to be considered Anticipated Device Effects.

18.3. Risks Associated with the Study Device(s)

There are no additional risks associated with the study devices that are above those of BSC commercially approved and market available CRT-D devices.

18.4. Risks associated with Participation in the Clinical Study

There are no additional risks that are associated with participation to the present study beyond those listed above, and all the visits associated to this protocol are performed as part of standard clinical practice.

18.5. Risk Minimization Actions

Additional risks may exist. Risks can be minimized through compliance with this protocol, performing procedures in the appropriate hospital environment, adherence to subject selection criteria, close monitoring of the subject's physiologic status during research procedures and/or follow-ups and by promptly supplying BSC with all pertinent information required by this protocol.

18.6. Anticipated Benefits

There may be no benefit to the subject. However, medical science and future subjects may benefit from their participation in this registry.

18.7. Risk to Benefit Rationale

The implantable CRT-D systems and accessories used for this Registry will be commercially available and are considered to be SOC for subjects indicated for such implants. The risks

involved with subject participation in this study are essentially the same as those for subjects not participating in the study.

19. Safety Reporting

19.1. Reportable Events by investigational site to Boston Scientific

It is the responsibility of the investigator to assess and report to BSC any event which occurs in any of following categories:

- All Serious Adverse Events
- All Adverse Device Effects
 - Events listed in the arrhythmia logbook, should be reported only if determined to be clinically significant by the investigator and/or delegated site staff (i.e. ATR, PMT, etc.)
 - Any new onset/diagnosis of VT/VF requiring anti-arrhythmic therapy, or per the PI, clinically worsening VT/VF requiring Therapy. (Appropriate VT therapy that is not considered clinically worsening per the PI is not to be reported).
- All Device Deficiencies
- Unanticipated Adverse Device Effects/Unanticipated Serious Adverse Device Effects
- All Heart Failure (HF) and All Cardiac related adverse events requiring IV or invasive therapy, including new onset cardiac events, or worsening in severity or frequency of pre-existing conditions.

An adverse event is deemed as a HF Event if the primary cause is HF and either of following conditions is met:

- In-patient hospitalization \geq 24 hours
- No hospitalization but received one or more IV medications including diuretics, inotropes, vasodilators, other parenteral therapy, or aquapheresis.

Adverse event collection begins after the subject signs the informed consent. Events which occur prior to the signing of the informed consent form, and per the investigator/delegated site staff are a result of the device implant procedure should not be reported. Even if such event requires a treatment that is executed after the informed consent is signed. (e.g. hematoma that requires intervention is not an adverse event as long as it does not worsen after consenting; infection at the incision site is not an adverse event as long as it does not worsen after consenting; planned medical procedure or lead revisions are not adverse events as long as the event is identified prior to the consent). These are considered preexisting conditions and are not reportable. If the event worsens after consenting and meets criteria for a reportable event then they must be reported (e.g. hematoma that is worsened and requires intervention; a new infection at the incision site or an infection that is worsened and requires

intervention). If the study subject is consented while still hospitalized from the initial device implant, and an event occurs which meets the definition of an SAE, the event must be reported.

The medical diagnosis should be reported for reported events. In case the diagnosis is not available, individual symptoms can be reported to fulfill reporting timelines. If a diagnosis becomes available at a later date, it should be added to the reported event.

If it is unclear whether or not an event fits one of the above categories, or if the event cannot be isolated from the device or procedure, it should be submitted as an adverse event and/or device deficiency.

Any AE required by the protocol, experienced by the study subject after informed consent and once considered enrolled in the study (as defined in study subject classification section), whether during or subsequent to the procedure, must be recorded in the eCRF.

Underlying diseases are not reported as AEs unless there is an increase in severity or frequency during the course of the investigation. Death should not be reported as an SAE, but should be reported as an outcome of an SAE and only one SAE should have the outcome documented as fatal (see Table 19.2-1 for AE definitions).

Refer to Section 18.3 for the known risks associated with the study device(s).

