9.2. Inclusion Criteria

Subjects who meet all of the following criteria (see Table 9.2-1) may be given consideration for inclusion in this Registry, provided no exclusion criterion (see Section 9.3) is met.

Table 9.2-1: Inclusion Criteria

Clinical Inclusion Criteria	
• Subject implanted or upgraded with an NG3 or NG4 CRT-D device based on BSC labelling for devices in specific geographies in conjunction with a quadripolar LV lead from any manufacturer• Subjects must be enrolled between 1 and 21 calendar days post CRT-D implantation procedure• Subject is age 18 or above, or of legal age and willing and capable to provide informed consent specific to each country and national laws• Subject is willing and capable of providing informed consent• Subject is willing and capable of complying with follow-up visits and procedures as defined by this protocol
------------------------------------	--

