12.1.3. NG4 PMCF Endpoint

12.1.3.1. Hypotheses

The NG4 PMCF Primary Endpoint was designed to evaluate the safety of the NG4 device when LV MSP is enabled. In the subjects included in the NG4 PMCF Cohort, the NG4 PG-related complication free rate (CFR) at 36 months will be used to evaluate the PMCF Primary Endpoint.

A PG-related Complication will be defined as those detectable adverse events that resulted in:

- Death
- Serious injury
- Correction of PG failure requiring invasive intervention
- Permanent loss of PG device function. Permanent loss of device function is defined as any Pulse Generator (PG) that reverts to Safety Core or any PG rendered unable to deliver pacing or shocks

Complications that are determined to be associated with the PG will be considered PG-related complications (PG) and count against the PMCF endpoint. Complications related to the LV, RV, RA leads will not be counted against the PMCF endpoint.

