12.1.3.2. Hypotheses

The following hypotheses will be evaluated to evaluate the safety of the NG4 device:

$$H_0: \text{PG-related CFR at 36 months} \leq 88.5\%$$

$$H_A: \text{PG-related CFR at 36 months} > 88.5\%$$

To ensure that the safety of the NG4 devices with LV MSP enabled is acceptable, the performance goal for this endpoint was based on the observed safety of prior approved Boston Scientific devices in the following studies: CAPTIVATE, LSS of 4-SITE, MADIT CRT, MultiSENSE, NAVIGATE X4. Prior devices in these studies have shown a PG-related complication-free rate of 98.5% through 36 months of follow-up. The performance goal of 88.5% was derived from the prior performance of 98.5% minus 10% to account for variability in the estimate. Expected performance of the NG4 device was based on the observed rate of prior devices.

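### Section 19.1 drops implant-procedure events that occur before consent even when they are treated on study, so the PMCF complication-free rate can only be too high, by an amount that depends on the consent day

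*Combined protocol and SAP*

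**What the plan says.** - **Start of collection (19.1).** "Adverse event collection begins after the subject signs the informed consent". Under 9.2, "Subjects must be enrolled between 1 and 21 calendar days post CRT-D implantation procedure".
- **Exclusion (19.1).** Events before consent that, in the judgement of the investigator or delegated staff, "are a result of the device implant procedure should not be reported". The next sentence extends this to treatment given on study: "Even if such event requires a treatment that is executed after the informed consent is signed". Hematoma and incision-site infection are among the examples of what is then not an adverse event.
- **Exceptions (19.1).** An event that worsens after consent and meets the reporting criteria must be reported. So must a serious adverse event that occurs after consent during the implant hospitalization.
- **Endpoint (12.1.3.1).** A PG-related complication is an adverse event that resulted in death, serious injury, invasive correction of PG failure, or permanent loss of PG function. Complications associated with the PG count. Lead complications do not.
- **Benchmark (12.1.3.2).** "Prior devices in these studies have shown a PG-related complication-free rate of 98.5% through 36 months of follow-up". The 88.5% goal is that rate minus 10 points.
- **Test (12.1.3.4, 12.2.2).** A Kaplan-Meier estimate at 36 months, with a one-sided 95% log-log lower limit compared with 88.5% and type I error held at 5%. No time origin is stated. Section 11.1 times the visits from enrollment.

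**The concern.** The endpoint is defined by the outcome of an adverse event, whereas 19.1 decides by date of occurrence whether there is an adverse event at all. Where the two meet, an outcome that happens under observation is lost.

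Take an implant-procedure complication judged PG-associated that appears on day 4 and reaches a qualifying outcome on day 15 without worsening in the sense of 19.1. With consent on day 3 it counts. With consent on day 5 it does not. The device history is the same; only the signature date differs.

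Other PG events before consent are missed for a simpler reason: collection has not begun, and nothing in the plan gathers them afterwards.

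This rate carries the study's only formal hypothesis test, and it is read against a historical figure whose counting window is not described. Every omission pushes the rate upward.

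**Working it through.** **1. The plan's own figure.** Section 12.1.3.3 needs 63 subjects at 36 months with 15% annual attrition: 63 / 0.85³ = 63 / 0.6141 = 102.6, rounded up to 103. In reverse, 103 × 0.6141 = 63.3. The 103 reproduces. The 63 cannot be reproduced because no target power is given.

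**2. Which events are lost.** Reading 19.1 and 12.1.3.1 together:

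| Event | Enters the PMCF endpoint? |
|---|---|
| PG-associated, implant-procedure, before consent, not worsening, qualifying outcome after consent | No, by the 19.1 exclusion |
| Other PG-associated event wholly before consent | No, collection has not started |
| Before consent, worsens after consent and meets the criteria | Reportable, so it can count if PG-associated |
| PG-associated, first occurs after consent, with a qualifying outcome | Yes |
| Lead complication | Never |

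Only the first two rows are at issue. The documents do not say whether pocket hematoma or infection is PG-associated.

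**3. Cost of one early event.** In the first three weeks nearly all 103 subjects are at risk, so one event moves the estimate by about 1/103 = 0.97 points. Ignoring censoring, with x events in n subjects, S = 1 − x/n and the lower limit is S^exp(1.645 × SE), where SE = √[x / (n(n − x))] / |ln S|.

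- n = 103, x = 6: S = 0.9417, SE = 0.0245/0.0600 = 0.408, limit = 0.9417^1.957 = 88.9% (passes).
- n = 103, x = 7: S = 0.9320, SE = 0.0266/0.0704 = 0.378, limit = 0.9320^1.862 = 87.7% (fails).

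One uncounted event can therefore change the result, but only at the margin.

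**4. Effect on the test.** The documents give no rate of PG failure before consent, so e is an assumption. If the true 36-month rate from implant is p, the rate measured after omission is p / (1 − e). Simulation: 103 subjects, exponential attrition of 15% per year, Kaplan-Meier with the planned limit, 8,000 runs per row.

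| True rate p | e (assumed) | Measured rate | Pass, early events counted | Pass, early events omitted |
|---|---|---|---|---|
| 98.5% | 0.5 points | 99.0% | 99.1% | 99.6% |
| 98.5% | 1 point | 99.5% | 99.6% | >99.9% |
| 88.5% | 0.5 points | 88.9% | 3.3% | 4.3% |
| 88.5% | 1 point | 89.4% | 3.9% | 6.1% |
| 88.5% | 2 points | 90.3% | 3.6% | 9.2% |
| 88.5% | 3 points | 91.2% | 3.7% | 15.6% |

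A separate run at 88.5% gave 5.7%, 9.7% and 14.3% for 1, 2 and 3 points omitted. I therefore quote about 6% to 15%, against about 4% when the events are counted.

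**The case against.** **Chronic safety may be the intent.** Section 8.3 speaks of chronic safety and 12.1.3.1 of safety with LV MSP enabled. MSP may be switched on at any time in the first 12 months, so peri-implant events can precede it. Counting from consent is defensible in a registry that consents after implant. This stands as a reason to label the rate, not to discard an outcome that occurs after consent.

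**The clause is narrow.** A reader might infer that any early generator problem escapes. The text does not support this. The exclusion covers results of the implant procedure. All device deficiencies are reportable, and an event that cannot be separated from device or procedure is to be submitted. Nor does the lead-revision example in 19.1 bear on this endpoint, since lead complications never count. An invasive procedure is also not enough in itself: the listed outcome is "Correction of PG failure requiring invasive intervention", and a hematoma or infection would have to qualify in another way, such as serious injury.

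**The window is short.** It is tempting to say that the rule removes the early risk period. It removes only implant to consent, at most 21 days, and enrollment may take place before discharge.

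**Early events cost less than late ones.** With events spread evenly over 36 months, 3, 4 and 5 events pass in about 98%, 67–71% and 8–11% of runs. Those figures overstate the cost of an omitted event, which falls when the risk set is full. Three spread events plus one early event pass in 86–89% of runs, and six early events pass in over 99%.

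**The assumed 1 to 3 points are large.** Section 12.1.3.2 implies 1.5% failure over the whole 36 months, so the assumption puts two-thirds to twice that before consent. This stands: the range is illustrative.

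**Two inferences are not shown.** A reader might suspect that sites time consent to suit the outcome, or that the benchmark used a different window. Section 11.2 requires no screening log, so timing could not be audited, but no passage shows either.

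**Conclusion.** The omission follows from the wording of 19.1 and 12.1.3.1 and runs in one direction. A PG-associated implant-procedure complication that occurs before consent cannot count, even when its qualifying outcome occurs on study, unless it worsens. Other PG events before consent are not collected.

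Its size cannot be derived from the documents. If NG4 performs at the expected 98.5%, the test passes in about 99% of runs or more either way, and an assumed 0.5 to 1 point of omission raises the measured rate to about 99.0% to 99.5%. If the true rate is 88.5% and 1 to 3 points of failure fall before consent, the false-pass rate is about 6% to 15%, above the 5% in 12.2.2. This assumes exponential attrition of 15% per year and that affected subjects stay in the cohort.

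The documents do not support a stronger conclusion that the formal test is compromised at the planned performance. The point is worth correcting because the rate will be reported as a 36-month device rate and compared with a benchmark whose window is unstated.

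**What to change.** For PMCF subjects:

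1. Amend 19.1 so that any PG-associated event whose 12.1.3.1 outcome occurs after consent is reported and counted, whenever it was first identified. State there whether pocket hematoma and infection are treated as PG-associated.
2. After consent, record from the chart any PG-associated events between implant and consent, and give a sensitivity rate from the implant date that includes them. Section 11.4.7 already collects the implant date. This rate still describes only patients who reached consent.
3. State the Kaplan-Meier time origin in 12.1.3.4, label the primary rate as counted from consent, and say in 12.1.3.2 whether the 98.5% used the same window.

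The cost is protocol wording and one eCRF item for about 103 subjects, with no added visit. The downside is that the reported rate may be slightly lower.
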